#### 12.3.1 Hypothesized Rates:

We hypothesize that metformin is superior to placebo for the primary endpoint controlling for possible use of fluvoxamine or ivermectin. Similarly, we hypothesize that fluvoxamine is superior to placebo for the primary endpoint controlling for possible use of metformin; and ivermectin is superior to placebo for the primary endpoint controlling for possible use of metformin. Let  $\pi_T$  and  $\pi_C$  denote the rate of the composite primary endpoint in the treatment and control groups, respectively. We will evaluate the following hypotheses:

#### $H_0: \pi_T \ge \pi_C$ versus $H_A: \pi_T < \pi_C$

The hypothesized marginal rate of the primary endpoint under placebo is 20%. The expected event rate for the primary outcome in the single medication treatment arms is 11% which corresponds to a relative risk reduction of 45%. To detect this effect with 80% power using a marginal test with 5% two-sided type I error requires 337 participants in each comparison group. To account for effects of other drugs used in combination, which may reduce the event rate of the control group, for the interim analysis plan, and for losses to follow-up, we plan to enroll 1,124 participants in total.

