Sample size estimates are based on a marginal test of metformin versus placebo comparison, controlling for fluvoxamine and ivermectin use, and selected to provide at least 80% power with

5% two-sided type I error rate for the target effect indicated by the event rates in the above figure and described in detail in subsection 12.3.1. The sample size estimates are also inflated by 11% and rounded to account for interim analysis plan (see subsection 13.4) and study withdrawals.

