# Factorial design maximizes the use of placebo

Each patient gets 2 types of pills		Metformin (n=563)	Placebo (n=187)	
	Fluvoxamine (n = 375)	Metformin / Fluvoxamine n =188 6% event rate if both effective	Fluvoxamine / placebo n=187 11% event rate	
	Ivermectin (n=375)	Metformin/Ivermectin n = 188 6% event rate if both effective	Ivermectin/Placebo n = 187 11% event rate	
		Metformin / placebo n = 187 11% event rate	Placebo / Placebo n=187 20% event rate	
	Total	563	561	

[figure not shown]
• If two medications are effective, we will have 80% power to detect a difference over placebo.

• If only one medication is effective, we will have 90% power to detect a difference over placebo.

• Assumes a 10% loss to follow-up rate.

These considerations result in a planned enrollment of 1,124 participants (187-188 in each arm). Because these sample size calculations are based on marginal tests, the actual power may be higher when based on the planned tests using adjusted logistic regression models adjusted for various predictive factors as described later.

VERSION 3.4

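### Protocol 12.3.1 attaches 80% power to 337 per group for 20% versus 11%; that effect needs about 253, and 337 gives about 90%

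*Protocol*

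**What the plan says.** Protocol 12.3.1 (Hypothesized Rates) gives two event rates for the primary endpoint: 20% under placebo and 11% in the single-drug arms, "which corresponds to a relative risk reduction of 45" per cent. It continues: "To detect this effect with 80% power using a marginal test with 5% two-sided type I error requires 337 participants in each comparison group". The next sentence goes from 337 per group to 1,124 in total by adding allowances for the interim plan, for losses and, first in its list, for combinations: "To account for effects of other drugs used in combination, which may reduce the event rate of the control group".

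The factorial table in 12.3 (Sample Size Assumptions) lists arms of 187 or 188 and, for the combination arms, "6% event rate if both effective". Below it stand two power statements, "If two medications are effective, we will have 80% power to detect a difference over placebo" and "If only one medication is effective, we will have 90% power to detect a difference over placebo", and a loss assumption: "Assumes a 10% loss to follow-up rate". The text of 12.3 adds: "The sample size estimates are also inflated by 11% and rounded to account for interim analysis plan" and for withdrawals.

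The section on prespecified analyses later replaces 1,124 with 1,350 on a different basis: a 35% relative reduction and a projected placebo rate.

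**The concern.** The 337 sentence states its power, alpha and sidedness, and the only rates given before it in 12.3.1 are 20% and 11%. The figure can therefore be checked from the document alone, and 337 looks too large for 80% power. It also conflicts with the table in 12.3, which promises 90% power when only one drug works, and that is the 20% versus 11% case.

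What is at stake is the stated rationale. From 12.3.1 alone a reader cannot tell whether 337 means 90% power for 20% versus 11%, or 80% power for a smaller effect when metformin also works. If it is the second, the combination effect is already inside 337, and the next sentence wrongly presents it as a later allowance. The prespecified analyses section justifies the increase to 1,350 partly by saying that the original size would be inadequate for a smaller effect, so what the original size delivered should be stated correctly.

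**Working it through.** **Inputs.** Control 20%, treated 11%, 80% power, two-sided 5%, 337 per group (12.3.1). Equal allocation across six arms (12.1 Randomization). Combination arms 6%, arms of 187 to 188, 10% loss (table in 12.3). Inflation of 11% (12.3).

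**Formula.** Pooled-variance normal approximation, with p̄ the mean of the two rates:

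n = [1.960 √(2p̄(1−p̄)) + z √(p1(1−p1) + p2(1−p2))]² / (p1−p2)², where z = 0.8416 for 80% power and 1.2816 for 90%.

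**Step 1: the printed figure from its own inputs.** For 20% versus 11%, p̄ = 0.155, √(2 × 0.155 × 0.845) = 0.5118 and √(0.16 + 0.0979) = 0.5078.

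- 80% power: (1.960 × 0.5118 + 0.8416 × 0.5078)² / 0.09² = 1.4305² / 0.0081 = 252.6, so 253.
- 90% power: (1.960 × 0.5118 + 1.2816 × 0.5078)² / 0.0081 = 1.6540² / 0.0081 = 337.7, so 338.
- Power at 337: Φ[(0.09 × √337 − 1.0031) / 0.5078] = Φ(1.278) = 89.9%. Exact binomial enumeration of the same test gives 90.3%.

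The choice of formula does not rescue 337 at 80% power:

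| Method | n per group |
|---|---|
| Arcsine | 249 |
| Unpooled | 250 |
| Pooled | 253 |
| Log-odds | 261 |
| Continuity-corrected | 275 |

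A one-sided 5% test needs 199. Dividing 5% by three would give 338, but the text states 5%. The printed figure exceeds its own requirement by 337/253 − 1 = 33%.

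**Step 2: comparison with the table in 12.3.** A fluvoxamine or ivermectin group has two arms, 188 + 187 = 375 enrolled. After 10% loss, 375 × 0.9 = 337.5. If only that drug works, the comparison is 20% versus 11%, and about 337 evaluable per group gives the table's 90%. The table does not print 337, so this match is inferred.

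**Step 3: where 337 gives 80%.** If metformin also works, the averages over the two arms are (20 + 11)/2 = 15.5% for control and (11 + 6)/2 = 8.5% for treated. Then p̄ = 0.12 and n = (1.960 × 0.4596 + 0.8416 × 0.4569)² / 0.07² = 1.2853² / 0.0049 = 337.1, with 80.0% power at 337. Applying the 45% reduction to 15.5% gives 8.525% and a size of 337.1 unpooled or 339.9 pooled; pooled power at 337 is then 79.7%.

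**Step 4: from 337 to 1,124.** 337/0.9 = 374.4 per two-arm group, and three such groups make 1,123. Using the 11% instead, 337 × 1.11 × 3 = 1,122. Loss alone therefore accounts for essentially the whole step, with no visible room for a combination or interim allowance. Starting from 253, the same step gives 253/0.9 × 3 = 843.

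**The case against.** The strongest reply is that 337 is a correct number with an incomplete label. Section 12.3 says the target effect is the one shown by the rates in the table and detailed in 12.3.1. The table includes the 6% combination arms, and averaging gives 15.5% versus 8.5%, for which 337 at 80% power is right. The table also prints both scenarios, 80% and 90%, just before 12.3.1. This is a plausible account of where 337 came from. It does not save the sentence, because 12.3.1 never states 15.5% or 8.5%.

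Second, nothing was numerically added twice: 337/0.9 × 3 already reaches about 1,124. That is right. The fault in the following sentence is one of description.

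Third, the two-arm reading is the fluvoxamine or ivermectin comparison, whereas 12.3 names metformin as the design basis. That comparison is three arms against three, about 562 enrolled and 505 evaluable per group. With all drugs working, the rates are (20 + 11 + 11)/3 = 14% versus (11 + 6 + 6)/3 = 7.67%, which needs about 377 per group for 80% power; 505 gives about 90%. If metformin alone works, 505 gives about 98%. This stands, and it is why the origin of 337 has to be confirmed by the sponsor and not assumed.

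Finally, there is no operational consequence. That is also right and limits the weight of the point.

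**Conclusion.** The concern holds, as a minor error in current protocol text. As written, 20% versus 11% at two-sided 5% needs about 253 per group for 80% power, and 337 gives about 90%. Either the effect or the power attached to 337 is mislabelled. This rests only on the rates, alpha and power printed in 12.3.1 and on equal groups, and it is certain.

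The explanation that 337 was sized for 15.5% versus 8.5% fits closely but is inferred. If it is right, the combination effect is already inside 337, and the sentence that adds it afterwards is wrong.

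The error is conservative: the original 1,124 was not too small for the effect stated. The current 1,350 rests on other assumptions and is not affected.

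**What to change.** In 12.3.1, state that 20% versus 11% needs about 253 per group for 80% power and that 337 evaluable per group gives about 90%, in line with the table in 12.3.

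Once the sponsor confirms how 337 was derived:

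1. If it was sized for the two-drug case, add that 337 gives 80% power for fluvoxamine or ivermectin when metformin is also effective (15.5% versus 8.5%).
2. Reword the next sentence so that the combination effect is not described as an allowance made after 337.
3. State what the 11% inflation covers, since 1/0.9 = 1.11 for the 10% loss already uses all of it.

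Label 12.3 and 12.3.1 as the original justification and refer to the prespecified analyses section for the current 1,350.

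The cost is wording and one confirmation from the sponsor. Enrolment, monitoring boundaries and analysis do not change.

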#### Prespecified analyses:

A detailed SAP will be submitted to the DSMB and updated if needed prior to analyses. The primary efficacy analysis for each study drug, metformin, fluvoxamine, and ivermectin, will be based on a logistic regression model with a main effect for the relevant drug controlling for study site, and use of the other study drugs. In particular, no interaction effects will be included in this analysis. Prespecified subgroup analyses

include: pregnant women, and individuals who have already received a SARS-CoV-2 vaccine.

The SAP includes a sample-size re-calculation procedure that was pre-specified for the analysis of futility and efficacy on the first 2/3 of participants enrolled. This procedure was presented to and approved by the DSMB at the DSMB analysis of futility and efficacy done after 2/3 of participants were enrolled, + 14 days of follow-up. The updated total sample size for the study based on this sample size re-calculation is 1,350. This re-estimation accounts for a larger portion of participants being vaccinated and greater prevalence of monocloncal antibody use after enrollment than was envisioned when the protocol was written in fall 2020, and the resultant impact on the event rate in the placebo control arm; and external evidence from the Together Trial indicating a 33% relative reduction from fluvoxamine for which the original sample size would not provide adequate power. The updated sample size is expected to provide 80% power to detect a 35% relative reduction from fluvoxamine, and similarly for ivermectin, while accounting for the recent impact of vaccination and therapeutics by using a projected estimate of the event rate for the primary outcome in the participants randomized to the placebo control arm.

#### 12.4 DSMB Monitoring Guidelines:

Safety, efficacy and futility will be monitored for both cohorts by an independent DSMB (more info below). Timing of analyses will be with respect to information time defined as the proportion of participants who have completed the primary endpoint follow-up interval relative to the planned sample size. Interim analyses will include all participants who have been followed for specified window so as to exclude participants with possibly yet to be determined outcome status and thereby ensure unbiased estimates of the primary event rate in each arm. Safety data will be reviewed regularly by the DSMB. The first interim analysis of efficacy data (Stage 1) will focus on safety and feasibility, while still allowing early stopping for efficacy. Subsequent interim analyses of efficacy data (Stage 2) will focus on efficacy, futility and any ongoing safety or feasibility concerns.

#### 12.4.1 Safety Monitoring:

Safety monitoring will be undertaken for each agent and combination. Regular reports will be provided to the DSMB at a mutually agreeable interval with an evaluation of safety outcomes that focus on comparisons of the frequency of deaths, SAEs and grade 4 events between the active treatment arms and placebo arm irrespective of attribution to study drug. Proportions and 95% exact confidence intervals will be used to summarize the results with unconditional exact tests and corresponding exact intervals to evaluate differences. Cumulative counts of adverse reactions and numbers of participants experiences and adverse reaction will be reported and compared similarly. Further safety assessments may be considered as demanded by the DSMB as well. The purpose of these reports is to catch any unexpected severe adverse reactions to metformin in the study populations. Formal statistical comparisons of safety endpoints using p-values will be undertaken at the request of the DSMB, and will otherwise not be reported.

12.4.2 Efficacy Monitoring:

### UNIVERSITY OF MINNESOTA 08December2021 COVID-OUT (formerly called MET-COVID) (MET29324)

VERSION 3.4

Efficacy monitoring will be undertaken for each of the three active agents against its control. Efficacy monitoring boundaries will be based on a Kim and DeMets alphaspending function that mimics O'Brien-Fleming boundaries (parameter value of 3). This upper boundary controls one-sided type I error at 2.5%, and will be modified according to the information fractions at the time of the actual analyses (defined by the current evaluable sample size / maximum sample size). The monitoring boundaries that will be provided to the DSMB for each cohort are reported in Table 2 and updated based on the actual sample size(s) available at the time of each analysis. The lower futility boundary will be treated as non-binding and supplemented with conditional power calculations in conjunction with the DSMB. This futility boundary is based on a Kim and DeMets beta spending function with a parameter value of 1.5. The lower Haybittle-Peto boundary for harm of -2.5 with 50% or less of the planned enrollment and -2.0 otherwise will be considered binding, though harm will be assessed in conjunction with safety data and may be declared by the DSMB despite the primary efficacy endpoint analysis not achieving this lower boundary. (Monitoring boundary calculations have been and will be carried out using the gsDesign package in R version 3.6.1 or newer.)

Following the sample size re-estimation procedure, the upper efficacy boundary will be calculated by spending the remaining type I error rate in proportion to the specified Kim and DeMets alpha-spending function where the information fraction is calculated with respect to the updated sample size. This approach corrects for over-spending alpha relative to the revised sample size and controls the overall one-sided type I error rate at the intended 2.5% level (or equivalently the two-sided 5% level).

**Table 2:** Monitoring Boundary Guidelines on Z-Score Scale. The futility boundary will beconsidered non-binding and supplemented by conditional power calculations. The harm boundarywill be considered binding.

Sample Size	62	386	774	1,124
Efficacy	3.737	3.116	2.461	2.001
Futility	-2.130	-0.093	1.087	2.001
Harm	-2.500	-2.500	-2.000	-2.000

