### VERSION 3.4

\*Updated sample size: 225 per arm, 1,350 total.

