## 17.0 Multi-Site Research

17.1 Study-Wide Number of Participants:

Up to 1,160 participants will be enrolled in the study to achieve the needed number of completed data sets.

17.2 Study-Wide Recruitment:

Each site will determine appropriate recruitment methods. A study brochure will be made available to all sites. Coordinators from the central site may help call positive patients at participating sites if a site becomes overwhelmed at any given time, given the rapidly changing geographic nature of this pandemic.

17.3 Communication with Sites:

All sites will be given access to study documents through the University of Minnesota BOX.

A project manager will be tasked with coordinate all communication, regulatory efforts, and ensuring sites are informed of study changes. The Project Manager will also work with the PI to ensure all non-compliance, adverse events, and other reportable events are reviewed and reported in accordance with local policies.

All study data will be entered into REDCap with each site being assigned a specific data access group so that staff at one site cannot see participant data from another site.

Personnel from all sites will participate in monthly progress meeting calls, which will include discussion of any problems including reportable events, interim results, and completion of the study. More frequent meetings may be planned, as necessary.

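### Table 2's monitoring boundaries do not follow the spending rule stated beside them: the interim values fit a maximum of 1,160, not 1,124, and efficacy values 3.737 and 2.001 fit neither

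*Protocol*

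**What the plan says.** Section 12.4.2 defines the efficacy boundary completely. It spends alpha by a Kim-DeMets function with parameter 3, and "This upper boundary controls one-sided type I error at 2.5" percent. The information fraction is "defined by the current evaluable sample size / maximum sample size". Futility is non-binding: "This futility boundary is based on a Kim and DeMets beta spending function with a parameter value of 1.5". The Table 2 values, which are to go to the DSMB, are to be "updated based on the actual sample size(s) available at the time of each analysis". After the sample size re-estimation the efficacy bound is found by "spending the remaining type I error rate in proportion to the specified Kim and DeMets alpha-spending function", with the fraction taken on the updated total.

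Table 2 gives these Z values:

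| Sample size | 62 | 386 | 774 | 1,124 |
|---|---|---|---|---|
| Efficacy | 3.737 | 3.116 | 2.461 | 2.001 |
| Futility | -2.130 | -0.093 | 1.087 | 2.001 |

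The protocol carries three totals. Section 12.3: "These considerations result in a planned enrollment of 1,124 participants". Section 17.1: "Up to 1,160 participants will be enrolled in the study". Section 5.1: "Updated sample size: 225 per arm, 1,350 total". The prespecified analyses under 12.3.1 confirm 1,350 as the current figure.

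**The concern.** The rule and the table stand in the same section, and the rule leaves nothing open on the efficacy side: alpha, spending function, information fraction and the treatment of futility are all given. The table should therefore follow from it, and it does not.

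These are the thresholds the protocol says the DSMB will receive. The two errors that fit no stated maximum both make the threshold too easy to cross: the first look is far below what the rule allows, and the final value is below what would hold 2.5%. The final analysis also depends on how much alpha was spent earlier. A table that cannot be reproduced leaves that amount uncertain unless the bounds actually used are on record. The analysis at two thirds of enrolment has already taken place according to the prespecified analyses under 12.3.1, so this concerns looks already taken.

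**Working it through.** **Inputs.** One-sided alpha 0.025, alpha-spending parameter 3, beta-spending parameter 1.5, non-binding futility, and looks at 62, 386, 774 and the maximum (12.4.2 and Table 2). Power of 80%, so beta = 0.20 (12.3). Section 12.4.2 itself gives no beta, so 0.20 is an assumption for the futility row only.

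**Formulas.** With t = n / N_max, the cumulative efficacy spend is 0.025·t³. Each bound is solved by recursive numerical integration under independent increments, ignoring the lower bound. Futility spends 0.20·t^1.5 under a drift chosen so that the two bounds meet at the last look.

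**Step 1: try to reproduce Table 2.**

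| | Look 1 | Look 2 | Look 3 | Final |
|---|---|---|---|---|
| t on 1,124 | 0.0552 | 0.3434 | 0.6886 | 1 |
| t on 1,160 | 0.0534 | 0.3328 | 0.6672 | 1 |
| Efficacy, printed | 3.737 | 3.116 | 2.461 | 2.001 |
| Efficacy, rule on 1,124 | 4.455 | 3.088 | 2.426 | 2.013 |
| Efficacy, rule on 1,160 | 4.475 | 3.116 | 2.461 | 2.009 |
| Futility, printed | -2.130 | -0.093 | 1.087 | 2.001 |
| Futility, rule on 1,124 | -2.102 | -0.040 | 1.158 | 2.013 |
| Futility, rule on 1,160 | -2.130 | -0.093 | 1.087 | 2.009 |

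On the table's own final column, 1,124, nothing in either row agrees. On 1,160, five of the six interim values agree to three decimals. That agreement also shows that the rule is implemented here as the sponsor implemented it.

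**Step 2: solve for the maximum implied by each printed value, allowing for rounding.** The value 3.116 needs a maximum of 1,159.8 to 1,161.1, and 2.461 needs 1,159.6 to 1,160.7. Both ranges contain 1,160. The value 2.001 needs about 1,242, a total the protocol does not give, and at that maximum looks 2 and 3 would be above 3.16 and 2.52.

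**Step 3: other readings.** Binding futility gives a final bound of 1.954 to 1.956. Spending parameter 2 gives 2.068 on 1,124 and 2.062 on 1,160. Keeping 3.737 at the first look and the rule thereafter gives 2.013 and 2.009. None of these returns 2.001 on these looks.

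**Step 4: alpha spent by the printed efficacy set, futility ignored.**

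| | Look 1 | Look 2 | Look 3 | Final |
|---|---|---|---|---|
| Printed bounds, 1,124 | 0.000093 | 0.00101 | 0.00750 | 0.02528 |
| Printed bounds, 1,160 | 0.000093 | 0.00101 | 0.00750 | 0.02546 |
| Rule, 1,124 | 0.0000042 | 0.00101 | 0.00816 | 0.02500 |
| Rule, 1,160 | 0.0000038 | 0.00092 | 0.00743 | 0.02500 |

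The excess is 0.02528 - 0.025 = 0.00028 on 1,124 and 0.02546 - 0.025 = 0.00046 on 1,160. At look 1 the printed value spends 22 to 24 times what the rule allows, although the amount itself is below 0.0001.

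**Step 5: the final bound that holds 0.025 after the printed interim bounds.** This is 2.007 on 1,124, 2.010 on 1,160 and 2.026 on 1,350. In the last case 0.025 - 0.00750 = 0.0175 remains to be spent at the final look. For comparison, the rule alone at 774/1,350 would have spent 0.00471.

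**The case against.** The strongest reply is that the text governs and the table does not. Section 12.4.2 calls the values guidelines, has them updated to the sample sizes at each analysis, and attaches the 2.5% claim to the spending function. The re-spending paragraph already requires a new final bound on the updated total, so nothing in version 3.4 proposes to test at 2.001 with 1,350 participants. If the text is followed, type I error is held.

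The size is also slight. The excess is at most 0.0005 one-sided, looks 2 and 3 are stricter than the rule on 1,124, and if the printed futility bounds were always obeyed the total would be about 0.023. The record of bounds used may already exist in DSMB reports or in the SAP, which is not at hand.

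All of this stands as a limit on the consequence. It does not explain the table. An update clause covers a change in sample size, but these values depart from the rule at the sample sizes printed above them. The re-spending rule needs the alpha already spent, and that depends on which bounds were in force. The figure of 0.023 cannot support the claim of control, because the protocol declares futility non-binding. The absence of a 1,350 column is not an error.

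**Conclusion.** The point holds: Table 2 is wrong as printed, with a small practical effect. Its interim values at 386 and 774, and its interim futility values, belong to a maximum of 1,160. Its 3.737 and 2.001 follow from the stated rule on neither 1,124 nor 1,160. The printed set exceeds the stated 2.5% by 0.0003 to 0.0005 one-sided. It should be corrected, but it does not threaten the trial's conclusions if the re-spending rule is applied.

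The efficacy results rest only on the rule in 12.4.2. The futility match also assumes beta = 0.20. That 1,160 is a leftover from a superseded design is an inference: the version history does not mention it, although 386 and 774 are 33.3% and 66.7% of 1,160. The 2.026 is an illustration on whole-trial counts. Monitoring is by drug, and the actual fractions depend on eligibility and on the modified intention-to-treat exclusions, so it should not be read as every drug's bound.

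**What to change.** - Mark Table 2 as superseded. Note that its efficacy values at 386 and 774 and its interim futility values correspond to a maximum of 1,160, and that 3.737 and 2.001 do not follow the stated rule.
- Do not substitute recomputed bounds for looks already taken. Record, for each drug, the evaluable number and the bounds actually used at each completed look.
- Derive the final bound at 1,350 from that record by the re-spending rule. It is 2.026 only if the printed bounds were used at 62, 386 and 774. Do not carry 2.001 forward.
- Change the total in 17.1 from 1,160 to 1,350.
- As a separate wording matter that carries no weight in this finding, reconcile the statement in 14.2 that the DSMB may recommend early stopping for safety alone with item B of that section, 12.4 and 12.4.2, which provide for efficacy monitoring and early stopping.

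The cost is a note on one table, one figure, one phrase and a record of bounds already used. Sample size and conduct do not change, and the final critical value is the one the re-spending rule already requires.
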